5.6 Primary Endpoint

5.6.1 Statistical Analysis for the Primary Estimand

The primary effectiveness analysis is the primary estimand of the primary endpoint. This analysis will be based on the FAS with missing data imputation as described in the Section 5.5.1. Percent change in body weight from baseline (month 0) to month 12 (visit 13) will be calculated for each study subject within the FAS per Section 4.5 and will be modeled using linear regression (Analysis of Covariance (ANCOVA)) with randomized treatment as a factor and baseline body weight (kg) as a covariate. The treatment difference between WMP + Rx and WMP alone will be estimated and reported together with the associated 95% confidence interval (CI) and corresponding p-value testing the null-hypothesis of no difference between treatment arms. Superiority for the primary endpoint will be considered established if the two-sided p-value is less than 5% and the estimated difference in mean weight change favors WMP + Rx.

5.6.1.1 Sensitivity Analysis of the Primary Estimand

A sensitivity analysis will be conducted using the multiple imputation approach as described by McEvoy [6] to impute missing body weight data at month 12 (visit 13). In this approach, month 12 measurements at visit 13 for non-retrieved drop outs will be imputed by sampling from values obtained from retrieved drop outs in the corresponding treatment arm and according to the timing of last available body weight. Multiple imputation will be performed separately for each

treatment arm following the three steps detailed in Section 5.5.1. The imputation model for this approach is a linear regression of body weight (kg) at visit 13 with gender (male/female), BMI (kg/m²) in categories 30-<35, 35-<40, ≥40 as factors and baseline body weight (kg), last available body weight prior to drop out, and month of last available body weight measurement prior to drop out as covariates. If timing by month is too restrictive, quarters (13 weeks), half-years (26 weeks), or excluding timing from the imputation model altogether will be used.

Analysis of percent change in body weight from baseline (month 0) and month 12 (visit 13) will be repeated and results summarized per the method outlined in Section 5.6.1. If this multiple imputation approach is not feasible, no sensitivity analysis will be done.

5.6.2 Statistical Analysis for the Secondary Estimand

The secondary estimand of the primary endpoint will address the efficacy of medication for chronic weight management if all subjects adhere to their randomized treatment (WMP + Rx or WMP). For the secondary estimand, the primary endpoint will be analyzed using a mixed model for repeated measurements (MMRM) including all subjects, but for subjects considered non-adherent to randomized treatment, only data prior to non-adherence will be used. Month 12 (visit 13) assessments for retrieved drop outs will not be used in this analysis. The MMRM for efficacy will only use assessments from subjects who are adherent to the randomized treatment until end of treatment, or up until the subject is considered non-adherent to the randomized treatment. Subjects in the WMP arm will be considered non-adherent if/when criterion 1 below is met. Subjects in the WMP + Rx arm will be considered non-adherent if/when criterion 1 or 2 is met:

1. Missing 4 SMA visits. In this case, the last assessment made prior to the 4th missed SMA visit will be used as the last assessment. This is also the case if, e.g., 4 SMA visits in a row are missed.
2. Period with no coverage of prescription claims according to PDC exceeds 20% of planned medication duration, or number of days from visit 1 to visit 13. For subjects that drop out early, the expected visit 13 date (derived from the subjects' planned SMA group visit) will be used to calculate planned study duration. The last assessment made prior to exceeding 20% of planned study duration with no prescription claims will be used as last assessment (as defined in Section 4.8.5).

The MMRM for efficacy will be fitted using % weight change with randomized treatment as factor and baseline body weight (kg) as covariate, all nested within visit. An unstructured covariance matrix for measurements within the same subject will be employed, assuming that measurements for different subjects are independent. From the model, treatment effect will be estimated and reported along with the associated 95% CI and corresponding p-value testing the null-hypothesis of no difference between treatment arms.

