5.2.2.3 Concomitant medications

Concomitant medications for medical conditions other than obesity are allowed in both treatment arms at the discretion of the study clinician, except for the use of glucagon-like peptide-1 receptor agonists (GLP-1 RAs) and sodium-glucose co-transporter 2 (SGLT-2) inhibitors for diabetes diagnosed during the study. Other than the medication prescribed by the study clinician for chronic weight management in the WMP + Rx arm (section 5.2.2.2), use of any medication, on- or off-label, for weight loss purposes is not allowed in either arm during the study. Through routine medication review during SMA study visits, use of medications that are not allowed per protocol (i.e., “disallowed”) will be identified and will be indicated in the eCRF. The subject will remain in the study.

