6.4.3 Secondary Estimand for the Primary Endpoint

The secondary estimand of the primary endpoint will address the efficacy of medication for chronic weight management if all subjects adhere to their randomized treatment (WMP + Rx or WMP). For the secondary estimand, the primary endpoint will be analyzed using a mixed model for repeated measurements (MMRM) including all subjects, but for subjects considered non-adherent to randomized treatment, only data prior to non-adherence will be used. Month 12 (visit 13) assessments for retrieved drop outs will not be used in this analysis. The MMRM for efficacy will only use assessments from subjects who are adherent to the randomized treatment until end of treatment, or up until the subject is considered non-adherent to the randomized treatment. Subjects in the WMP arm will be considered non-adherent if/when criterion 1 below is met. Subjects in the WMP + Rx arm will be considered non-adherent if/when criterion 1 or 2 is met:

1. Missing 4 SMA visits. In this case, the last assessment made prior to the 4th missed SMA visit will be used as the last assessment. This is also the case if, e.g., 4 SMA visits in a row are missed.
2. Period with no coverage of prescription claims according to PDC exceeds 20% of planned medication duration, or number of days from visit 1 to visit 13. For subjects that drop out early, the expected visit 13 date (derived from the subjects' planned SMA group visit) will be used to calculate planned study duration. The last assessment made prior to exceeding 20% of planned study duration with no prescription claims will be used as last assessment.

The MMRM for efficacy will be fitted using % weight change with randomized treatment as factor and baseline body weight (kg) as covariate, all nested within visit. An unstructured covariance matrix for measurements within the same subject will be employed, assuming that measurements for different subjects are independent.

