6.4.4 Supplementary Analyses

The analyses of % weight change will be supplemented with a completer analysis based on the subset of subjects with month 12 (visit 13) body weight data who were adherent to the randomized treatment.

Completer analysis

In the context of this supplementary analysis, completers will be defined as subjects with month 12 (visit 13) body weight data who adhered to randomized treatment up to and including visit 13. Adherence is defined as for the secondary estimand for the primary endpoint in section 6.4.3, i.e., subjects in the WMP arm will be considered non-adherent if/when criterion 1 above is met and subjects in the WMP + Rx arm will be considered non-adherent if/when either criterion 1 or 2 above is met. As an example, a subject in the WMP + Rx arm that misses visit 10, 11, and 12, but attends all other visits and is covered by prescription claims for at least 80% of the planned study duration, is considered a completer in this context if month 12 (visit 13) weight data are available.

This analysis will use the same ANCOVA model described for the primary estimand analysis of the primary endpoint (section 6.4).

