Appendix 1-1: Time and Events Schedule

Study NN8022-4432	Screening and Randomization	Weight Management Program											
		V2	V3	V4	V5	V6	V7	V8	V9	V10	V11	V12	V13
Visit (V)	V1	V2	V3	V4	V5	V6	V7	V8	V9	V10	V11	V12	V13
Timing of visit (months)	0	1	2	3	4	5	6	7	8	9	10	11	12
Visit window (days)	0	±14	±14	±14	±14	±14	±14	±14	±14	±14	±14	±14	-14, +28
SUBJECT-RELATED INFORMATION AND ASSESSMENTS													
Informed consent	X												
Demography ^a	X												
Inclusion criteria	X												
Exclusion criteria	X												
Randomization	X												
Medical history/concomitant illness	X												
Concomitant medication	X												
Disallowed medication ^b		X	X	X	X	X	X	X	X	X	X	X	X

Study NN8022-4432	Screening and Randomization	Weight Management Program											
		V2	V3	V4	V5	V6	V7	V8	V9	V10	V11	V12	V13
Visit (V)	V1												
Timing of visit (months)	0	1	2	3	4	5	6	7	8	9	10	11	12
Visit window (days)	0	±14	±14	±14	±14	±14	±14	±14	±14	±14	±14	±14	-14, +28
EFFICACY													
Height	X												
Body weight	X	X	X	X	X	X	X	X	X	X	X	X	X ^c
WPAI-SHP	X						X						X
WLQ-8	X						X						X
SMA attendance		X	X	X	X	X	X	X	X	X	X	X	X
SAFETY													
Adverse event	X ^d	X	X	X	X	X	X	X	X	X	X	X	X
REMINDERS													
HbA1c	X ^e												
Urine pregnancy test	X ^f												
Schedule nutritionist appointment	X												
Refer to exercise physiologist	X												

^a Demography consists of date of birth, sex, ethnicity, and race.

Novo Nordisk

Protocol No. NN8022-4432
UTN: U1111-1218-8104

^b Disallowed medications include GLP-1 RAs or SGLT-2 inhibitors for diabetes and any medication on- or off-label prescribed for weight loss other than the medication prescribed by the study clinician for chronic weight management (section 5.2.2.3). Use of these medications will be assessed during routine medication review at SMAs and entered into the eCRF.

^c If a subject does not attend the SMA at visit 13, a stepwise approach to obtaining weight data will be applied to obtain a month 12 weight measurement (-14 days, +28 days from scheduled month 12/visit 13): calling subject in for a month 12/visit 13 weight measurement, extract recent weight data from the electronic medical record, or use recent subject-reported weight.

^d Screening and randomization are one visit. Serious adverse event and pregnancy collection will begin after informed consent and randomization.

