1.0 INTRODUCTION

This document describes the Statistical Analysis Plan (SAP) for Protocol Number NN8022-4432, Real world effectiveness of combining an employer-based weight management program with medication for chronic weight management in employees with obesity – a pragmatic randomized trial. This is a one-year, single-center, randomized, open label, parallel-group, pragmatic clinical trial (PCT) comparing Cleveland Clinic's existing Integrated Medical Weight Management Program (WMP) combined with medication for chronic weight management versus Cleveland Clinic's existing Integrated Medical WMP with no medication for weight management in subjects with obesity.

This SAP is based on the most recent version of the protocol: Version 1.0, October 10, 2018.

Protocol History:

Number	Version	Date
1.0	Original Protocol	October 10, 2018

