4.2.2 Secondary Estimand

The secondary estimand for body weight loss, categorical weight loss, and PROs is an “if all subjects had adhered” estimand (also known as an “efficacy” estimand). This estimand will quantify the average treatment effect of an employer-based WMP combined with medication for chronic weight management compared to the employer-based WMP alone after 12 months, in all randomized subjects had they adhered to their randomized treatment for the entire planned study duration as defined in Section 5.6.2.

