5.6.3 Supplementary Analyses

The analysis of % weight change will be complemented with the following supplementary analyses. Analyses #3 and #4 will assess the potential impact of altering the mode of administering the SMAs, from on-site to virtual, during the trial in response to the COVID-19 outbreak.

Supplementary Analysis #1 (Completer analysis)

In the context of this first supplementary analysis, the analysis population will be defined as subjects in the FAS with month 12 (visit 13) body weight data who adhered to randomized treatment up to and including visit 13. Adherence is defined as for the secondary estimand for the primary endpoint in Section 5.6.2, i.e., subjects in the WMP arm will be considered non-adherent if/when criterion 1 above is met and subjects in the WMP + Rx arm will be considered non-adherent if/when either criterion 1 or 2 above is met. As an example, a subject in the WMP + Rx arm that misses visit 10, 11, and 12, but attends all other visits and is covered by prescription claims for at least 80% of the planned study duration, is considered a completer in this context if month 12 (visit 13) weight data are available. This analysis will use the same ANCOVA model described for the primary estimand analysis of the primary endpoint (Section 5.6.1).

Supplementary Analysis #2

For the second supplementary analysis, the analysis population will be defined as subjects in the FAS who remain in the CC EHP for the entirety of their study participation. Subjects who leave the Cleveland Clinic Employee Health Plan (CC EHP) and end study participation or leave the CC EHP but continue to attend SMAs and take study medication if in the WMP + Rx arm will be excluded from the analysis. Analysis of this subset of subjects will include missing body weight data imputation as described in the Section 5.5.1. Change in percent body weight will be analyzed and presented as described for the primary estimand analysis of the primary endpoint (Section 5.6.1).

Supplementary Analysis #3

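### The secondary (all-adherent) estimand classes subjects who take disallowed weight-loss medication as adherent and keeps their weights

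*SAP*

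**What the plan says.** SAP 4.2.2 sets the secondary estimand as the effect "in all randomized subjects had they adhered to their randomized treatment for the entire planned study duration as defined in Section 5.6.2". The section it points to gives two criteria, and protocol 6.4.3 gives the same two. Criterion 1 is four missed SMA visits. Criterion 2 is time without prescription coverage above 20% of the planned duration.

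- WMP arm: "Subjects in the WMP arm will be considered non-adherent if/when criterion 1 below is met" (SAP 5.6.2).
- WMP + Rx arm: "Subjects in the WMP + Rx arm will be considered non-adherent if/when criterion 1 or 2 is met" (protocol 6.4.3).

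The completer analysis inherits this. Protocol 6.4.4 states: "Adherence is defined as for the secondary estimand for the primary endpoint in section 6.4.3". SAP 5.6.3 restates the rule in its own words: "subjects in the WMP arm will be considered non-adherent if/when criterion 1 above is met".

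The comparator is described in SAP 1.0 as the "existing Integrated Medical WMP with no medication for weight management in subjects with obesity". Protocol 5.2.2.3 says that, apart from the study clinician's obesity prescription in WMP + Rx, "use of any medication, on- or off-label, for weight loss purposes is not allowed in either arm during the study". It also bars GLP-1 receptor agonists and SGLT-2 inhibitors for diabetes diagnosed during the study, and keeps users in the study. Footnote b of protocol Appendix 1-1 says how use is captured: "Use of these medications will be assessed during routine medication review at SMAs and entered into the eCRF". The schedule marks this check at visits 2 to 13.

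Two places in the SAP deal with the resulting data. Section 5.9 tabulates use overall and by arm. Section 5.4 summarizes major deviations by type, treatment violations among them. Neither changes which weights enter an analysis.

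**The concern.** The secondary estimand asks what the treatment difference would be if each subject kept to the assigned treatment. In the control arm that treatment has two parts: attending the programme and taking no weight-management drug. The adherence rule checks only the first part.

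The rule is also one-sided. Criterion 2 removes weights from WMP + Rx subjects who lose drug coverage, but nothing removes weights from WMP subjects who gain a drug. Both depart from the randomized contrast.

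The same definition serves the secondary-estimand weight analysis (SAP 5.6.2), the responder and PRO analyses (5.7.2, and the month 6 version in 5.7.3), and the completer analysis and Supplementary Analysis #4 (5.6.3). The completer analysis and Supplementary Analysis #4 therefore cannot serve as a check on this point. At stake is whether the reported efficacy estimate answers the question set for it.

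**Working it through.** **Step 1: follow one subject through the rules.** Take a WMP subject who starts a weight-loss drug on their own, attends at least 9 of the 12 SMAs and has a month 12 weight.

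| Rule | Result |
|---|---|
| Protocol 5.2.2.3 | Use is barred, recorded in the eCRF, and the subject stays in the study |
| SAP 5.6.2, criterion 1 | Not met: at most 3 SMAs missed |
| SAP 5.6.2, criterion 2 | Does not apply to WMP |
| MMRM | All weights kept, including those on the drug |
| Completer analysis (SAP 5.6.3, #1) | Counts as a completer |
| SAP 5.4 and 5.9 | Use is tabulated; no estimate changes |

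**Step 2: reproduce the plan's own figure, to fix the effect scale.** Protocol 6.3.1 uses a 4-point difference, SD 10%, 100 subjects per arm and a two-sided 5% t-test, and states power of 0.80. Recalculation gives 0.804. Table 6-1 therefore applies the 4 points as the difference across all 200 randomized subjects.

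**Step 3: effect among adherent subjects, two readings.**
- If 4 points is the effect in adherent subjects, δ = 4.
- If 4 points is already net of drop-out as protocol 6.3.1 describes it (50% complete with full effect, 25% retrieved with half, 25% not retrieved with none), the retained share is 0.50 × 1 + 0.25 × 0.5 + 0.25 × 0 = 0.625, and δ = 4/0.625 = 6.4.

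**Step 4: shift in the contrast.** Let p be the share of analysed WMP subjects on a disallowed drug with the full effect δ, and q the share of WMP + Rx subjects on one that adds an effect e. Then

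shift = −δp + eq.

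The first term shrinks the contrast and the second inflates it. The documents give none of p, q and e, so the net sign is open. For the first term alone, with p assumed:

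| p (assumed) | δ = 4 | δ = 6.4 |
|---|---|---|
| 5% | 4 × 0.05 = 0.20 | 6.4 × 0.05 = 0.32 |
| 10% | 4 × 0.10 = 0.40 | 6.4 × 0.10 = 0.64 |

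**Step 5: compare with sampling error.** With SD 10% and 50 adherent subjects per arm (50% of 100), SE = 10 × √(2/50) = 2.00. The shifts are then 0.20/2.00 = 0.10 SE to 0.64/2.00 = 0.32 SE. If the MMRM recovered the information of all 100 per arm, SE = 10 × √(2/100) = 1.41 and the largest shift is 0.64/1.41 = 0.45 SE.

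**The case against.** The adherence rule is explicit, prespecified and identical in protocol and SAP, and SAP 4.2.2 refers to it for the meaning of adherence. On that view the estimand is whatever 5.6.2 makes it. This stands to a degree: the two documents do not contradict each other, and the point asks for an added intercurrent event. But a definition that counts a barred drug as adherence to a drug-free comparator works against the estimand's own question.

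Protocol 5.2.2.3 keeps users in the study. That governs follow-up and suits the primary estimand. It does not settle which weights belong in a hypothetical one.

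Use is likely to be low. Protocol section 1 says the health plan does not cover these drugs, and protocol 4.2.4 excludes subjects with diabetes. This stands and limits the size of the problem. Later use, or a weaker drug, would also give less than the figures above. The 0.64 needs 10% use together with the 6.4-point reading. That reading is contestable, because protocol 6.3.1 says the effect scenarios came from product labels.

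A reader might infer that disallowed medication is left out of the SAP altogether. It is not: sections 5.4 and 5.9 report it, so the extent of contamination will be visible.

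A reader might also see an error in SAP 4.8.5, where overlapping supply is carried forward with no same-drug condition although switching is allowed. The text does not support that. The worked example there is a refill, so the case of a switch is at most ambiguous. A same-drug rule would also bring miscounts of its own: coverage would be lost for subjects who finish the earlier drug, while unused supply after a plain stop would still count. It merits a clarifying sentence and is not part of this point.

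**Conclusion.** The point holds as an omission in the definition behind the secondary estimand. A subject taking disallowed medication, most clearly a WMP subject on a weight-loss drug, stays adherent, and all that subject's weights stay in the MMRM and, with a month 12 weight, in the completer analysis. For GLP-1 receptor agonists or SGLT-2 inhibitors taken for newly diagnosed diabetes, the ground is the protocol's own ban and not the wording of the comparator.

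Under assumed use of 5% to 10% in WMP, the contrast falls by about 0.2 to 0.4 points at a 4-point effect, and by up to 0.64 at 6.4. That is a fraction of a standard error. These rates are illustrations, since the documents give none.

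Two stronger inferences fail. The secondary estimate cannot be called biased toward no difference, because use in WMP + Rx pushes the other way. The primary result is also not in doubt: the primary estimand applies regardless of adherence, so the primary analysis, the confirmatory test and the power are untouched, and SAP 3.2 makes all secondary endpoints supportive. This is a low-priority, cheap improvement.

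**What to change.** In SAP 5.6.2 add a third data cut-off for both arms: the last assessment used is the one before the visit at which disallowed medication, as listed in SAP 5.9, is first recorded. Then:

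- carry it through the secondary-estimand weight, categorical and PRO analyses and Supplementary Analysis #4;
- edit the completer definition in SAP 5.6.3 separately, because it restates criteria 1 and 2;
- align protocol 6.4.3 and 6.4.4, or document the departure in the SAP.

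The cost is SAP wording and some programming on data already collected at each SMA. It changes an analysis rule only; what subjects may take and how they are managed stay as they are. There are two downsides. The MMRM loses a few assessments. The documents also record no start date for disallowed use, so the last weight kept may already have been measured on the drug.

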5.6.3 Supplementary Analyses

The analysis of % weight change will be complemented with the following supplementary analyses. Analyses #3 and #4 will assess the potential impact of altering the mode of administering the SMAs, from on-site to virtual, during the trial in response to the COVID-19 outbreak.

Supplementary Analysis #1 (Completer analysis)

In the context of this first supplementary analysis, the analysis population will be defined as subjects in the FAS with month 12 (visit 13) body weight data who adhered to randomized treatment up to and including visit 13. Adherence is defined as for the secondary estimand for the primary endpoint in Section 5.6.2, i.e., subjects in the WMP arm will be considered non-adherent if/when criterion 1 above is met and subjects in the WMP + Rx arm will be considered non-adherent if/when either criterion 1 or 2 above is met. As an example, a subject in the WMP + Rx arm that misses visit 10, 11, and 12, but attends all other visits and is covered by prescription claims for at least 80% of the planned study duration, is considered a completer in this context if month 12 (visit 13) weight data are available. This analysis will use the same ANCOVA model described for the primary estimand analysis of the primary endpoint (Section 5.6.1).

Supplementary Analysis #2

For the second supplementary analysis, the analysis population will be defined as subjects in the FAS who remain in the CC EHP for the entirety of their study participation. Subjects who leave the Cleveland Clinic Employee Health Plan (CC EHP) and end study participation or leave the CC EHP but continue to attend SMAs and take study medication if in the WMP + Rx arm will be excluded from the analysis. Analysis of this subset of subjects will include missing body weight data imputation as described in the Section 5.5.1. Change in percent body weight will be analyzed and presented as described for the primary estimand analysis of the primary endpoint (Section 5.6.1).

Supplementary Analysis #3

For the third supplementary analysis, a subgroup analysis will be performed based on the FAS and using the imputed weight data derived for the analysis of the primary estimand for the primary endpoint (Section 5.5.1). This analysis will use the same ANCOVA model described for the primary estimand analysis of the primary endpoint (Section 5.6.1), but with the addition of an interaction term composed of randomized treatment and mode of MN12 SMA administration (on-site or virtual) to the regression model. This interaction term will serve as a test for whether or not the observed treatment effect was consistent between those subjects who had an on-site MN12 SMA and those subjects who had a virtual MN12 SMA (H_0 : treatment effect [on-site MN12 SMA] = treatment effect [virtual MN12 SMA]). In the event of a significant interaction effect, the treatment difference between WMP + Rx and WMP alone will be presented as

described for the primary estimand analysis of the primary endpoint but stratified by mode of MN12 SMA administration.

Supplementary Analysis #4

In the context of this fourth supplementary analysis, the analysis of the secondary estimand of the primary endpoint will be repeated and results summarized per the method outlined in Section 5.6.2, but with the additional exclusion of body weight data collected after the transition to virtual SMAs. This analysis will use a MMRM and all body weight assessments from subjects who were adherent to the randomized treatment until end of treatment or until the transition to virtual SMAs (whichever occurred first), or up until the subject was considered non-adherent to the randomized treatment prior to the transition to virtual SMAs per the adherence criteria noted in Section 5.6.2.

